### **3.3.4 Rationale for Biomarker Assessments**

#### **Pharmacodynamic biomarkers**

Pharmacodynamic biomarkers, including  $\beta 7$  receptors on peripheral gut homing leucocytes serum and soluble MAdCAM-1, will be measured to assess the target engagement and pharmacological effect of etrolizumab and to understand if the PK/PD relationship between etrolizumab exposure and receptor occupancy of the  $\beta 7$  expressing cells in the blood (and potential variability) observed in the adult UC patients are consistent with the pediatric patients with UC or CD. This will help to identify the serum concentration required for maintaining receptor occupancy in the pediatric population and to support the dose selection for Phase III pediatric clinical trial. PD sample time points have been aligned with the proposal for the EMA health authority.

#### **Inflammatory biomarkers**

All patients enrolled in the study will have fecal calprotectin and serum C-reactive protein (CRP) samples collected at the baseline (predose) and over the study period to assess the effect of etrolizumab treatment in reducing levels of inflammatory biomarkers.

Associations between exposure and these inflammatory biomarkers may also be explored.

## **4. MATERIALS AND METHODS**

### **4.1 PATIENTS**

A minimum of 12 patients with UC and CD from 4 years to  $<18$  years of age will be enrolled in the study. There will be at least 4 children from 4 years to  $<12$  years of age with evaluable PK profiles, which is a study obligation according to the health authority requirement.

#### **4.1.1 Inclusion Criteria**

Patients must meet the following criteria for study entry:

- Signed Informed Consent Form by parent or legal guardian
- Age of 4 years to  $<18$  years at the time of signing the Informed Consent Form
- Ability to comply with the study protocol, in the investigator's judgment
- Weight of 13 kg or more

- Diagnosis of UC or CD confirmed by biopsy and established for  $\geq 3$  months (i.e., after first diagnosis by a physician according to American College of Gastroenterology [ACG] guidelines) prior to screening
- Inadequate response, loss of response or intolerance to prior immunosuppressants and/or corticosteroid treatment and/or anti-TNF therapy
- For patients with UC: moderately to severely active UC as determined by an MCS of 6–12 with an endoscopic subscore  $\geq 2$  (within the last 12 months prior to screening) and a rectal bleeding subscore  $\geq 1$
- For patients with CD: moderately to severely active CD as determined by a Pediatric Crohn's Disease Activity Index (PCDAI) score of  $> 30$  at baseline
- Must meet the following surveillance colonoscopy requirements:
  - Document evidence of surveillance for dysplasia every 1 to 2 years, beginning approximately 7 to 10 years after their initial diagnosis
- For postpubertal females of childbearing potential: agreement to remain abstinent (refrain from heterosexual intercourse) or use acceptable contraceptive methods during the treatment period and for at least 24 weeks after the last dose of etrolizumab.

A female is considered to be of childbearing potential if she is postmenarcheal, has not reached a postmenopausal state ( $\geq 12$  continuous months of amenorrhea with no identified cause other than menopause), and has not undergone surgical sterilization (removal of ovaries and/or uterus).

Examples of acceptable contraceptive methods include bilateral tubal ligation, male sterilization, combined oral contraceptive pill or transdermal patch, spermicide and barrier [condoms], intrauterine device, implants for contraception, injections for contraception [with prolonged release], hormonal vaginal device (see [Appendix 6](#)).

The reliability of sexual abstinence should be evaluated in relation to the duration of the clinical trial and the preferred and usual lifestyle of the patient. Periodic abstinence (e.g., calendar, ovulation, symptothermal, or postovulation methods) and withdrawal are not acceptable methods of contraception.

- For male patients: agreement to remain abstinent (refrain from heterosexual intercourse) or use contraceptive measures, and agreement to refrain from donating sperm, as defined below:

With female partners of childbearing potential or pregnant female partners, men must remain abstinent or use a condom during the treatment period and for at least 24 weeks after the last dose of study drug to avoid exposing the embryo to study drug. Men must refrain from donating sperm during this same period.

The reliability of sexual abstinence should be evaluated in relation to the duration of the clinical trial and the preferred and usual lifestyle of the patient. Periodic abstinence (e.g., calendar, ovulation, symptothermal, or postovulation methods) and withdrawal are not acceptable methods of contraception.

#### **4.1.2        Exclusion Criteria**

Patients who meet any of the following criteria will be excluded from study entry:

##### **4.1.2.1      Exclusion Criteria Related to Inflammatory Bowel Disease**

- Prior extensive colonic resection, subtotal or total colectomy, or planned surgery
- Past or present ileostomy or colostomy
- Diagnosis of indeterminate colitis
- Suspicion of ischemic colitis, radiation colitis, or microscopic colitis
- Diagnosis of toxic megacolon within 12 months of initial screening visit
- Abdominal abscess
- A history or current evidence of colonic mucosal dysplasia
- Patients with fixed symptomatic stenosis of the intestine
- Patients with history or evidence of adenomatous colonic polyps that have not been removed.
- Patients who are not up to date on vaccinations per the local vaccine schedule will be excluded.

##### **4.1.2.2      Exclusion Criteria Related to Ulcerative Colitis**

- Severe extensive colitis per investigator judgment that colectomy is imminent OR the patient has two of the following five symptoms at screening or baseline visit:
  - 6 bowel movements daily with obvious blood
  - Abdominal examination worrisome for imminent surgery
  - Persistent fever
  - Tachycardia
  - Anemia (hemoglobin < 8 g/dL)

##### **4.1.2.3      Exclusion Criteria Related to Crohn's Disease**

- Sinus tract with evidence for infection (e.g., purulent discharge) in the clinical judgment of the investigator
- Short-bowel syndrome
- Evidence of abdominal or perianal abscess
- Expected to require surgery to manage CD-related complications during the study

##### **4.1.2.4      Exclusion Criteria Related to Prior or Concomitant Therapy**

- Any prior treatment with anti-integrin agents (including natalizumab, vedolizumab, and efalizumab)
- Any prior treatment with ustekinumab
- Any prior treatment with anti-adhesion molecules (e.g., anti-MAdCAM-1)
- Any prior treatment with rituximab

- Use of IV steroids within 30 days prior to screening with the exception of a single administration of IV steroid
- Use of agents that deplete B or T cells (e.g., alemtuzumab or visilizumab) within 12 months prior to Day 1, with the exception of AZA and 6-MP
- Use of cyclosporine, tacrolimus, sirolimus, or mycophenolate mofetil (MMF) within 4 weeks prior to Day 1
- Use of other biologics (e.g., anti-TNF) within 8 weeks before dosing, unless drug level is below detectability before completion of the 8-week interval
- Chronic nonsteroidal anti-inflammatory drug (NSAID) use (Note: occasional use of NSAIDs and acetaminophen [e.g., headache, arthritis, myalgias, or menstrual cramps] and aspirin up to 325 mg daily is permitted.)
- Patients who are currently using anticoagulants, including but not limited to warfarin, heparin, enoxaparin, dabigatran, apixaban, rivaroxaban. (Note that antiplatelet agents, such as aspirin up to 325 mg daily or clopidogrel, are permitted.)
- Apheresis (i.e., Adacolumn® apheresis) within 2 weeks prior to Day 1
- Received any investigational treatment including investigational vaccines within 12 weeks prior to Day 1 of the study or 5 half-lives of the investigational product, whichever is greater
- History of moderate or severe allergic or anaphylactic/anaphylactoid reactions to chimeric, human, or humanized antibodies, fusion proteins, or murine proteins or hypersensitivity to etrolizumab (active drug substance) or any of the excipients (L-histidine, L-arginine, succinic acid, polysorbate 20)

#### **4.1.2.5 Exclusion Criteria Related to General Safety**

- Pregnant or lactating
- Lack of peripheral venous access
- Congenital or acquired immune deficiency
- Hospitalized (other than for elective reasons) during the screening period
- Inability to comply with study protocol, in the opinion of the investigator
- Significant uncontrolled comorbidity, such as cardiac (e.g., moderate to severe heart failure New York Heart Association [NYHA] Class III/IV), pulmonary, renal, hepatic, endocrine, or GI disorders (excluding UC and CD)
- Neurological conditions or diseases that may interfere with monitoring for PML
- History of demyelinating disease
- Clinically significant abnormalities on the screening PML Subjective Checklist
- History of major neurological disorders, including stroke, multiple sclerosis, brain tumor, neurodegenerative disease, or poorly controlled epilepsy
- History of alcohol, drug, or chemical abuse <6 months prior to screening
- Conditions other than UC or CD that could require treatment with >10 mg/day of prednisone (or equivalent) during the course of the study

- Presence of metal in the body that could pose a hazard during any potential scanning in patients for whom a magnetic resonance imaging (MRI) scan is considered unsafe
- History of cancer, including hematologic malignancy, solid tumors, and carcinoma in situ, within 5 years before screening with the following caveats:
  - Local basal or squamous cell carcinoma of the skin that has been excised and is considered cured is not exclusionary.
  - A history of chronic myelogenous leukemia, hairy cell leukemia, melanoma, renal cell carcinoma, or Kaposi sarcoma is exclusionary, irrespective of the duration of time before screening.
  - History of a cervical smear indicating the presence of adenocarcinoma in situ (AIS), high-grade squamous intraepithelial lesions (HSIL), or cervical intraepithelial neoplasia (CIN) of Grade >1 is exclusionary, irrespective of the duration of time before screening.

  - Patients with a chest X-ray (posteroanterior and lateral) within 3 months of Day 1 suspicious for pulmonary TB are not eligible for this study.
- Suspicion of active TB on chest radiograph (X-ray, posteroanterior and lateral) taken within 3 months of randomization
- History of recurrent opportunistic infections and/or history of severe disseminated viral infections (e.g., herpes)
- Opportunistic infection within 3 months before screening
- Any current or recent signs or symptoms (within 4 weeks before screening and during screening) of infection, except for the following:
  - Minor infections (e.g., common cold) that have, in the investigator's judgment, completely resolved prior to Day 1
  - Fungal infections of the nail beds
  - Oral or vaginal candidiasis that has resolved with or without treatment prior to Day 1
- Any major episode of infection requiring treatment with IV antibiotics within 8 weeks prior to screening or oral antibiotics within 4 weeks prior to screening
  - Treatment with antibiotics as adjunctive therapy for UC/CD in the absence of documented infection is not exclusionary.
- Received a live attenuated vaccine within 4 weeks prior to Day 1
- History of organ transplant

#### **4.1.2.7 Exclusion Criteria Related to Laboratory Values (at Screening)**

- Serum creatinine >1.5 times upper limit of normal (ULN)
- ALT or AST >3 ULN, or alkaline phosphatase >3 ULN, or total bilirubin >2.5 ULN (unconjugated hyperbilirubinemia that is associated with known Gilbert's syndrome is not an exclusion criterion)
- In patients with diabetes: glycosylated hemoglobin (HbA1c) > 8.0%
- Platelet count <100,000/mL

- Hemoglobin <8 g/dL
- Absolute neutrophil count <1500/mL
- Absolute lymphocyte count <500/mL

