#### **Exclusion Criteria Related to Laboratory Values (at Screening)**

- Serum creatinine >1.5 times upper limit of normal (ULN)
- ALT or AST >3 ULN, or alkaline phosphatase >3 ULN, or total bilirubin >2.5 ULN (unconjugated hyperbilirubinemia that is associated with known Gilbert's syndrome is not an exclusion criterion)

- In patients with diabetes: glycosylated hemoglobin (HbA1c) > 8.0%
- Platelet count <100,000/mL
- Hemoglobin <8 g/dL
- Absolute neutrophil count <1500/mL
- Absolute lymphocyte count <500/mL

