#### **4.5.1        Informed Consent Forms and Screening Log**

Written informed consent and minor assent for participation in the study must be obtained before performing any study-specific screening tests or evaluations. Informed Consent Forms and Assent Forms for enrolled patients and for patients who are not subsequently enrolled (e.g., screen failures, eligible patients who choose not to enroll) will be maintained at the study site.

All screening evaluations must be completed and reviewed to confirm that patients meet all eligibility criteria before enrollment. The investigator will maintain a screening log to record details of all patients screened and to confirm eligibility or record reasons for screening failure, as applicable.

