#### **4.5.6 Laboratory, Biomarker, and Other Biological Samples**

Laboratory assessments will be performed as indicated on the Schedule of Assessments (see [Appendix 1](#)). All laboratory assessments will be sent to one or more central laboratories for analysis with the exception of CMV. If there is suspicion for clinically significant CMV colitis, a colonic biopsy sample should be sent for CMV evaluation,

which may be conducted locally depending on local requirements for the timing of the test result. Urine pregnancy testing will be conducted locally.

On days of study drug administration, laboratory samples should be drawn before the administration of study drug. Laboratory assessments will include the following:

- Hematology (hemoglobin, hematocrit, platelet count, RBC count, WBC count, absolute differential count [neutrophils, eosinophils, lymphocytes, monocytes, basophils, other cells], mean corpuscular volume, mean corpuscular hemoglobin, mean corpuscular hemoglobin concentration, and RBC distribution width)
- Serum chemistries, including liver function tests (sodium, potassium, chloride, bicarbonate, glucose, blood urea nitrogen, creatinine, calcium, phosphorus, magnesium, total and direct bilirubin, total protein, albumin, alanine aminotransferase, aspartate aminotransferase, lactate dehydrogenase, alkaline phosphatase, creatine phosphokinase, and uric acid)
- Urinalysis
- Tuberculosis: The PPD skin test and QuantiFERON-TB Gold are acceptable screening assays for latent *Mycobacterium TB* infection.
  - A positive PPD tuberculin skin test reaction is considered  $\geq 5$  mm. Patients with a history of *Bacille Calmette-Guerin* (BCG) vaccination should be screened using the QuantiFERON-TB Gold test only. An indeterminate QuantiFERON-TB Gold test should be repeated. A positive QuantiFERON-TB Gold test or two successive indeterminate QuantiFERON-TB Gold test results should be considered a positive diagnostic TB test. An indeterminate QuantiFERON-TB Gold test followed by a negative QuantiFERON-TB Gold test, should be considered a negative diagnostic TB test.
  - If a negative TB screening test has been documented within 3 months of screening, no new test is needed.

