- CMV testing of colonic biopsy sample: ONLY necessary if there is suspicion for clinically significant CMV colitis. Colon biopsy sample (to be obtained at the base of the ulcer) will be analyzed for histologic presence of CMV, but otherwise is not necessary for inclusion in the study. Analysis should be performed locally if possible or can be sent to a central laboratory if necessary.

Routine hematology and biochemistry tests can be used to satisfy inclusion/exclusion criteria if samples are collected within the 35-day window between screening and baseline. If these tests are not planned hematology and biochemistry samples should be collected at screening and analyzed accordingly.

The total volume of blood loss for laboratory assessments (including all safety, PK/PD, and efficacy samples) does not exceed the per-visit and cumulative-visit recommendations of the National Institutes of Health for the expected average weights of the patient population.

For sampling procedures, storage conditions, and shipment instructions, see the laboratory manual.

Unless the patient gives specific consent for his or her leftover samples to be stored for optional exploratory research (see Section 4.5.10), biological samples will be destroyed when the final Clinical Study Report has been completed, with the exception of stool and serum samples collected for PK, PD, or immunogenicity analysis samples, which will be destroyed no later than 5 years after the final Clinical Study Report has been completed.

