### **5.1.1.1      Serious Infections**

#### **5.1.1.1.1    Progressive Multifocal Leukoencephalopathy**

##### **Background**

PML is a potentially fatal neurological condition linked to reactivation of a polyomavirus (JC virus) and active viral replication in the brain. Cases of PML have been reported in patients with CD and multiple sclerosis who received concomitant treatment with the anti- $\alpha$ 4 integrin natalizumab and immunosuppressives. Integrin  $\alpha$ 4 $\beta$ 1, which is inhibited by natalizumab, is a pleiotropic integrin that is believed to facilitate T cell migration into the CNS. Inhibition of integrin  $\alpha$ 4 $\beta$ 1 is thought to reduce (CNS) immune surveillance and facilitate development of PML.

*According to the U.S. Package Insert for vedolizumab, which selectively impedes lymphocytes trafficking into gut tissue by specifically blocking only the  $\alpha$ 4 $\beta$ 7 integrin and not the  $\alpha$ 4 $\beta$ 1 integrin, one case of PML in an ENTYVIO (vedolizumab)-treated patient with multiple contributory factors has been reported in the post-marketing setting (e.g., HIV infection with a CD4 count of 300 cells/mm^3 and prior and concomitant immunosuppression) to date. Although unlikely, a risk of PML cannot be ruled out.*

Etrolizumab targets cells expressing the  $\beta$ 7 integrin ( $\alpha$ 4 $\beta$ 7 and  $\alpha$ E $\beta$ 7 cells) and not  $\alpha$ 4 $\beta$ 1 cells. Despite the lack of theoretical or experimental evidence for a specific role of  $\beta$ 7 integrins in leukocyte homing to the CNS and given the observation of PML risk with natalizumab, the Sponsor will continue to conduct extensive risk-monitoring procedures during this study. There have been no cases of PML in patients treated with etrolizumab.

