### **9.2 PROTOCOL DEVIATIONS**

The investigator should document and explain any protocol deviations. The investigator should promptly report any deviations that might have an impact on patient safety and data integrity to the Sponsor and to the IRB/EC in accordance with established IRB/EC policies and procedures. The Sponsor will review all protocol deviations and assess whether any represent a serious breach of Good Clinical Practice guidelines and require reporting to health authorities. As per the Sponsor's standard operating procedures,

prospective requests to deviate from the protocol, including requests to waive protocol eligibility criteria, are not allowed.

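### The platelet, neutrophil and lymphocyte exclusion limits are printed per mL, so read literally these three safety exclusions would almost never apply

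*Combined protocol and SAP*

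**What the plan says.** Section 4.1.2.7 lists the laboratory values that exclude a patient at screening. Three are cell counts: "Platelet count <100,000/mL", a neutrophil limit, and "Absolute lymphocyte count <500/mL". The synopsis repeats the list with the same unit, for example "Absolute neutrophil count <1500/mL". Nowhere does the document restate these limits per microlitre, per mm³ or per litre.

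The criteria bind. Section 4.5.1 states: "All screening evaluations must be completed and reviewed to confirm that patients meet all eligibility criteria before enrollment". Section 9.2 adds that "prospective requests to deviate from the protocol, including requests to waive protocol eligibility criteria, are not allowed".

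On where the counts come from, Section 4.5.6 says "All laboratory assessments will be sent to one or more central laboratories for analysis with the exception of CMV", but the same section also says "Routine hematology and biochemistry tests can be used to satisfy inclusion/exclusion criteria" when the samples fall in the screening window. Section 9.4 describes about 20 sites and the use of accredited local laboratories for routine monitoring.

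**The concern.** A count per mL is 1000 times the same count per mm³, so a limit with the wrong denominator is wrong by three orders of magnitude. As printed, the limits are so low that a patient with a severely reduced count would still pass.

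These are operative safety criteria. Section 5.1 names eligibility criteria that screen out at-risk patients as one principle of the safety plan, and Section 1.4 says this is the first pediatric study of the drug, with risk and benefit in children unknown.

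Low counts are foreseeable in this population. Section 1.1 names bone marrow suppression as a side effect of 6-MP, AZA and MTX. Section 4.1.1 makes failure of or intolerance to prior immunosuppressants one route to entry, and Section 4.4.1 lets these drugs continue. The rule in Section 3.1 that a third failure of the laboratory criteria makes a screen failure would also hardly ever operate for these counts.

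**Working it through.** **Inputs**

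- Printed limits (Section 4.1.2.7 and synopsis, identical in both): platelets 100,000/mL, neutrophils 1500/mL, lymphocytes 500/mL.
- Conversion: 1 mL = 1000 mm³ = 1000 microlitres, so count per mm³ = count per mL ÷ 1000.
- Scale check: the only other blood-cell count in the document. Section 5.1.1.1.1, citing the label of another anti-integrin, describes a patient who developed PML with "HIV infection with a CD4 count of 300 cells/mm"³ among the contributory factors.

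**Conversion of the printed limits**

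| Count | Printed, per mL | ÷ 1000 = per mm³ | Same digits read per mm³ |
|---|---|---|---|
| Platelets | 100,000 | 100 | 100,000 |
| Neutrophils | 1500 | 1.5 | 1500 |
| Lymphocytes | 500 | 0.5 | 500 |

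The last column is 1000 times the third in every row. It shows the effect of one possible reading and is not a statement of the intended limit.

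**Scale check for lymphocytes**

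300 cells/mm³ × 1000 = 300,000 cells/mL, and 300,000 ÷ 500 = 600. CD4 cells are a subset of lymphocytes, so that patient's total lymphocyte count was at least 600 times the printed limit. The printed lymphocyte criterion would not have excluded that patient.

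The document gives no comparison count for platelets or neutrophils, and no reference ranges or distributions for any of the three. That these exclusions would almost never apply is therefore a qualitative judgement from the size of the converted limits. No frequency can be computed.

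**Is the unit a conversion artefact?**

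- The micro sign survives next to mL elsewhere: in the serum concentration in Section 1.3 and the exposure figures in Section 3.3.2.
- Dropping the sign from a per-microlitre unit would leave a per-litre unit. To give what is printed, the sign must have been replaced by the letter m in all six entries (3 limits × 2 lists).
- The synopsis repeats the body list, so the six entries are not independent confirmations.

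**The case against.** The strongest objection is that the unit may have been altered when the text was read from the PDF, in which case the plan contains no error. Replacing the micro sign by m is a one-character change that would turn a per-microlitre limit into exactly what is printed. The places where the sign survives are micrograms in running prose. No microlitre unit appears anywhere in the text, so nothing shows how that token would have been handled. The eligibility lists have other oddities consistent with lost symbols: the liver-test limits lack the multiplication sign printed in Section 5.3.5.8, and the bowel-movement item in Section 4.1.2.2 has no comparison sign. This objection stands in part. It cannot be settled without the source page, so confidence is medium and checking that page is the first step of the fix.

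The second objection is that no consequence is shown. That is correct. Nothing indicates that any site, laboratory or eligibility check applied a per-mL limit, and experienced staff may well have read the limits in a conventional unit. The hemoglobin limit and the immune-deficiency exclusion still operate, as do scheduled on-treatment hematology and the evaluation of new cytopenias in Section 5.1.1.5. On-treatment monitoring begins after exposure, however, and does not replace a screening limit.

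The third objection is that one CD4 count from one patient on another product is thin support. It bears on one of the three limits and says nothing about screening in this trial. It serves only as a check of scale; the conversion does not depend on it.

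**Conclusion.** The concern holds for the text as printed. The three limits equal 100 platelets, 1.5 neutrophils and 0.5 lymphocytes per mm³, and nothing in the document corrects or restates the unit. Followed exactly, as Sections 4.5.1 and 9.2 require, three safety exclusions become practically inoperative.

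The factor of 1000 rests on the assumption that the same figures were meant per mm³. If per mL was meant, the limits stand as converted. The conclusion also assumes that the source page prints per mL. No number of affected patients is claimed, and the PK and PD analyses in Sections 6.4 and 6.5 are untouched. The point should be fixed because it concerns operative safety criteria and the correction is small.

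**What to change.** 1. Check the source file for a lost or substituted micro sign in both lists. If the source does not read per mL, the point closes.
2. If it reads per mL, the sponsor should reconcile the denominator of the three counts in Section 4.1.2.7 and in the synopsis with the intended unit and with the unit in which the laboratories report.
3. Confirm which unit the eligibility checks used, for routine hematology results accepted under Section 4.5.6 as well as central laboratory results.
4. Only if those checks used the printed per-mL limits, review the screening counts of enrolled patients.

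No threshold is proposed here; the limits are for the sponsor to state.

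The cost is a text correction to six entries and one confirmation. The conditional review would cover about 24 planned patients (Section 3.1).
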